**TABLE 1. CYP2C19 genotypes, inferred phenotypes, and population frequencies**

ALLELEx	GENOTYPE/ACTIVITY	PHENOTYPE b	FREQUENCY
*1/*1	Wild Type (WT) / 2 active alleles	NM	39%
*1/*n	Heterozygous WT/1 active, 1 LOF allele	IM	20%
*2/*2 or *n/*n	Homozygous variant/2 LOF alleles	PM	1.7%
*1/*17	Heterozygous WT/1 active, 1 GOF allele	RM	28%
*17/*17	Homozygous variant/2 GOF alleles	UM	5.3%
*2/*17	Heterozygous; 1 LOF/ 1 GOF allele	?	5.6%

a\*2, \*3, \*8, or \*9 refer to loss-of-function (LOF) alleles, n refers to any of the LOF alleles

bAbbreviations: GOF –gain of function; NM—normal metabolizer; IM – intermediate metabolizer; PM – poor metabolizer; RM—rapid metabolizer; UM—ultra-rapid metabolizer

[figure not shown]
Given that the frequencies of homozygous variants are relatively rare, our analyses will focus on three main phenotype groups from the five CYP2C19 phenotypes listed in **Table 1**. These will be those individuals carrying a LOF allele (hereafter referred to as PMs), those with no variant alleles (hereafter referred to as NMs) and those carrying a gain of function allele (hereafter referred to as RMs). As noted, those who are \*2/\*17 will not be included in the primary analysis since the relevant phenotype is not clear. In secondary analyses we will associate outcomes with the five phenotypes listed in table 1.

***Efficacy of PPIs depends on plasma concentrations and CYP2C19 genetic variation.*** Studies in adults and children report that the efficacy of PPIs to treat GERD and related conditions are closely linked to plasma concentrations . Numerous studies in adults have shown that CYP2C19 variants markedly influence the pharmacokinetics and pharmacodynamics of PPIs (see reviews 6,16-18,23,31-33). H pylori cure rates are significantly higher among PMs compared to RMs  and higher doses of PPI are required to treat H pylori in RMs. There are fewer studies in children. Although earlier studies suggested that CYP2C19 variants had little effects on PPI PK in children, recent studies support a role for CYP2C19 variants.

***Long-term PPI use is associated with increased risk of adverse events.*** PPIs are among the most commonly prescribed drugs in the world owing to their efficacy and perceived safety. However, there is mounting evidence that long-term use of PPIs are associated with a number of significant adverse effects including gastric and respiratory infections, bone fractures and kidney disease. Additionally, there is evidence suggesting that higher daily PPI doses and/or the degree of acid suppression increase risk, thereby supporting a role for CYP2C19 genetic variation contributing to adverse events.

***Infections*** Chronic gastric acid suppression reduces the effectiveness of the pH barrier in the stomach to protect against infections from ingested bacteria and viruses, and alters the gastric flora of the gastrointestinal tract.  Studies in adults and children have reported increased risk of intestinal infections with *Salmonella*, *Clostridium difficile*, *Shigella*, *Campylobacter*, *Streptococcus*, *Lactobacilli* and fungus (see reviews40-46). Importantly, the dysbiosis associated with PPI depends on the dose or degree of acid suppression. In a pharmacoepidemiologic study comparing the risks of nosocomial *Clostridium difficile* infection (CDI) among patients receiving gastric acid suppression treatment, increasing the intensity of suppression (no suppressive treatment; H2 antagonists (HTA), daily PPI and twice or more PPI administration/day) was associated with increased CDI 47 (See **Figure 1**).

**Figure 1. Odds ratio for CDI with gastric suppression therapy**

If aspirated during reflux episodes, infected gastric media may increase the risk of upper respiratory infections. A prospective study of 46 children with chronic cough or wheezing demonstrated the association of nonacid reflux with higher rates of positive lung bronchoalveolar lavage cultures in children. Additionally, acid suppression therapy in children resulted in bacterial overgrowth including *Staphylococcus* and *Streptococcus*, and full-column non-acid reflux was associated with bacterial overgrowth in the lung, which was proportional to acid suppressor dose. Several studies have reported associations between the chronic use of PPIs and upper respiratory infections and community-acquired pneumonia in infants, children and adults.

Additionally, the risk of community-acquired pneumonia was associated with higher PPI doses. A recent, randomized, placebo controlled clinical trial of the efficacy of lansoprazole (LZ) to improve asthma symptoms in 300 children with poorly controlled asthma reported increased prevalence of upper respiratory infection, sore throat and bronchitis in participants taking LZ compared to placebo. In an ancillary study we documented that children with asthma receiving LZ and phenotyped as PM had a 3-fold higher incidence of respiratory infections compared children who did not carry a LOF allele. Specifically, the risks of upper respiratory infections, OR=2.96 (95% CI, 0.86-2.79;  $p < 0.05$ ) and sore throat, OR=2.94 (95% CI, 1.23-7.05;  $p < 0.05$ ), were higher among PMs compared to other phenotypes (NM+RM) and to placebo; blood levels of lansoprazole were also higher among PM compared to NM/RM. These data are the first to show that CYP2C19 genetic variation is linked to PPI-associated respiratory infections.

**Bone fracture.** Vitamin/mineral malabsorption has been associated with increased risk of bone fractures in the elderly, which in some studies were related to higher daily doses of PPI (See review). PPI use has been associated with bone fractures in young adults but not in children younger than 18 years old. However, [name] and colleagues, studying the efficacy of lansoprazole in childhood asthma, reported that 5 children in the PPI group reported fractures compared to one child in the placebo arm suggesting that PPI-associated fractures may occur in children. The mechanism underlying PPI-associated bone fractures is not known. However, it may involve acid suppression and increasing gastric pH as H2 antagonist use has also been associated with bone fractures.

**Acute and chronic kidney disease.** Early case and anecdotal reports suggest associations between PPI use and acute kidney injury (AKI). More recent studies link PPI use with the risk of chronic kidney disease (CKD) and with progression to end-stage renal failure (ESRD). Twice -daily PPI dosing was associated with a higher risk of CKD compared to once-daily dosing supporting the idea this adverse event is dose related. Interestingly, a population-based cohort study reported hazard ratios for the risk of kidney injury were 2.9, 2.6, 2.5 and 2.4 for omeprazole, lansoprazole, rabeprazole and pantoprazole, respectively, thus demonstrating similar propensities among PPI to associate with AKI. The same study estimated the risk of drug rechallenge among patients with AKI following initiation of PPI treatment. PPI-associated kidney disease presents a real dilemma for physicians especially in treating elderly patients who require acid suppression treatment. Our study is important because it proposes that PP-associated kidney disease may be minimized by genotype-guided dosing.

The primary adverse effect phenotypes for focus in this proposal will be increased rate of gastrointestinal and pulmonary/upper respiratory infections, bone fracture and adverse kidney outcomes. These have been selected for focus because there is strong association data between PPI use (and PPI dose) and these adverse phenotypes, they have been observed in the age ranges that will represent the majority of our population, and they are computable phenotypes.

While other adverse effects such as suggestions of risk of myocardial infarction, and dementia have been associated with PPIs, we will not focus on these outcomes as the power in our study will not be sufficient to detect these outcomes. Additionally, for dementia the risk has been observed in PPI users over the age of 75, and we are likely to have limited numbers of patients in our analysis of this age group.

**Case for CYP2C19 genotype-guided PPI dosing.** The data above provide substantial evidence for the link between CYP2C19 genotype, PPI pharmacokinetics, efficacy and adverse effects. Use of PPIs has increased dramatically in the last decade, driven in part by an impression that they are “benign drugs”. As a result they are often prescribed as long term therapy in multiple different patient populations. It is not uncommon for patients to be on PPI therapy for multiple years or even “indefinitely”, despite no clear indication being present.

As described in this application, long-term PPI use has been associated with potentially serious adverse events. Recent high profile publications have increased awareness among clinicians of potential risks of PPIs, and the need for more rational use and dosing. In many cases data suggest the risk of adverse effects are dose related, which implies that safety of these drugs can be improved through rational dosing based on CYP2C19 genotype. Although the case for pharmacogenetic testing of CYP2C19 to guide PPI therapy has been made recently, additional evidence is needed. This project is significant because it will add to the evidence of associations between CYP2C19 genotype and adverse outcomes to PPI therapy and will also prospectively test the hypothesis that genotype-guided PPI dosing is safer than conventional dosing in children and adults. It will also provide practical experience on the clinical implementation of CYP2C19 genotype-guided PPI dosing.

**Advancing the IGNITE network.** There are multiple levels at which this proposal advances the IGNITE network, and genomic medicine implementation more broadly. First, this is a collaborative effort between three groups, two groups funded within the IGNITE network (UF and Vanderbilt) and an IGNITE affiliate member institution (Nemours Children's Health System). Such collaborative efforts highlight the impact of the IGNITE network in pulling together these groups and creates an outstanding paradigm for further advancing the network by extending to the IGNITE affiliate members. Such an effort would likely not have occurred in the absence of IGNITE, highlighting the “greater than the sum of its parts” goals for an NIH-funded network. Importantly, the preliminary data for this proposal come from the Nemours investigators, and this mechanism provides a means of exploiting the power created by the IGNITE network to rapidly move forward with enhanced generation of data to support clinical utility and to advance genomic medicine implementation. Additionally, this proposal includes significant representation of pediatric patients, who to our knowledge are not represented in the current IGNITE network portfolio. This proposal also allows for UF and Vanderbilt to expand upon a gene for which they have significant clinical implementation experience, and extend to an additional, very commonly used drug class. Additional evidence that documents potential clinical utility of use of CYP2C19 genotype to guide therapy with multiple drugs will further advance the arguments with payers for the value and logic of a pre-emptive genotyping approach that will have value across multiple different drugs.

**(b) Innovation.** This proposal is innovative in that we will employ existing clinical CYP2C19 genotype data in the electronic health record, along with the clinical record of over 10,000 patients with genotype and PPI exposure to add significantly to the literature on CYP2C19 genotype and adverse outcome risk. Given conventional study design limitations, major research funders (ie, NIH, PCORI) are increasingly recognizing the promise of novel “big data” approaches to advance biomedical research. Our proposal’s technical innovation is in applying a “big data” approach, incorporating EHR, and outcomes data across UFHealth and Vanderbilt to help clarify the relationship with PPI use, CYP2C19 genotype, and clinical outcomes. The conceptual innovation of our proposal lies in the use of “real world” patient data, rather than conventional cohort or RCT data that generally have strict inclusion/exclusion criteria. This allows us to inform treatment in real world patients not represented in RCTs. We will also utilize a pragmatic trial design that will allow us to simultaneously document the feasibility of genotype-guided PPI dosing, and whether such an approach is as effective and safe as usual care, with potential to document the clinical benefits.

### **(c) Approach**

#### **Preliminary Data in support of this proposal**

Patients with CYP2C19 genotype and PPI exposure in the EHR at UFHealth and Vanderbilt. At UFHealth and Vanderbilt, more than 16,000 patients to date have undergone CYP2C19 testing, with 10,185 being prescribed a PPI. Of these approximately 20% are PMs (1 or 2 LOF alleles), 41% are NMs, and 33% are RMs (1 or 2 GOF alleles), and approximately 7% with genotype combinations with unknown phenotypes. The goal of this analysis will be to evaluate the relationship with overall metabolism (poor vs normal vs rapid) with clinical outcomes. The hypothesis is that PMs will have increased rates of acid suppression and associated increased rates of bone fractures, infection, and chronic kidney disease and dementia while RMs are more likely to develop refractory GERD (inadequate acid suppression) and lower rates of PPI-related complications.

Lansoprazole pharmacokinetic data and CYP2C19 genotype. Table 2 demonstrates the relationship between plasma drug concentrations and CYP2C19 genotype.

**Table 2. Comparison of lansoprazole plasma concentrations by CYP2C19 phenotype.**

Phenotype	Alleles	Number Participants	Mean $\pm$ LZ Con. ng/ml
NM	*1/*1	11	199 $\pm$ 137
IM	*1/*2 or *3	13	303 $\pm$ 165
RM	*1/*17	11	168 $\pm$ 146
UM	*17/*17	2	156 $\pm$ 123
?	*2/*17	4	201 $\pm$ 57.1

The data in Table 2 were collected from children with asthma taking a 30-mg lansoprazole (LZ) dose daily for 6 months. Blood was drawn 2 hours after the final dose which corresponds to time at which blood levels peak after an oral dose. Note that compared to individuals with the NM phenotype, LZ concentrations were higher in carriers of one loss-of-function allele (\*1/\*2 or \*3; PM) indicating decreased clearance. Carriers of \*17 gain-of- function allele (RM) had lower LZ concentrations compared to NMs or PMs, indicating higher clearance. Though the number of participants is small, \*17/\*17 participants (UM) had the lowest LZ concentrations; and for \*2/\*17 participants levels were similar to \*1/\*1 alleles (NM phenotype). These preliminary data support the hypothesis that CYP2C19 variations influence the PK of LZ in children and that CYP2C19 genotype can be used to discriminate metabolizer phenotypes.

Association Between CYP2C19 Phenotype and pH Testing Outcomes in Children taking PPIs. Esophageal pH probe testing is commonly performed in children to assess the efficacy of proton pump inhibitor (PPI) medication therapy for gastroesophageal reflux disease (GERD). We hypothesized that CYP2C19 enzyme GOF phenotype among children who have undergone esophageal pH probe testing while on PPI therapy would be associated with pH probe acid exposure outcomes. Tissue collected during pH probe testing was genotyped in 74 children using Taq Man techniques. Children with the RM phenotype had a poorer response to PPI compared to PM and NM phenotypes (**Table 3**). Our data support that CYP2C19 variants influence response to PPI and suggest that genotype-guided PPI dosing may avoid pH probe testing in some children. We also hypothesize the same would be observed in adults.

Table 3. CYP2C19 phenotype and PPI efficacy				
CHARACTERISTIC	GOF (N=21)*	LOF (N=53)	RR (CI)	P value
Caucasian, %	76	71		NS
Male, %	66	62		NS
Mean Age at pH test, years(SD)	8(4.6)	8(4.9)		NS
Mean PPI Dose(SD), mg/kg	1.26(0.45)	1.00(0.62)		NS
% time pH < 4	5.71	2.67	1.6 (1.1-2.3)	<0.005
Mean Acid clearance (SD)	181(271)	107(158)	2.2 (1.5-3.2)	<0.0001
Mean Number Acid Reflux Episodes(SD) in 24 hrs	25(35)	24(32)	0.71-1.5	NS

\*GOF = Gain-of-function--\*17 carriers, LOF = Loss-of-function carriers + no variant alleles

#### Comparison of CYP2C19 SNP Frequencies in Controls vs. Children Undergoing Fundoplication.

**Table 4** shows allele frequencies of CYP2C19 \*2 (LOF) and \*17 (GOF) in children who were on PPIs and who had undergone fundoplication surgery were compared to controls, who were asthmatic patients who participated in the PPI trial . DNA for genotyping was obtained from saliva samples collected from controls, and for cases was obtained from tissue samples collected from children during undoplication surgery. The minor allele frequency of the \*2 (A) allele (PM or IM phenotypes) was underrepresented in the fundoplication cohort compared to controls and the minor allele for the \*17 allele (T) (RM phenotype) was over-represented in the fundoplication cohort compared to controls. These data suggest that RMs are more likely to be undertreated with usual doses of PPI therapy and as a result are subjected to invasive management approaches. In contrast, those with the PM phenotype are effectively treated with a usual dose and so are under-represented in the surgical group. These data could be inferred to suggest that genotype-guided PPI dosing could result in dose increases in RMs, which may have the potential to reduce the number of children who would need to undergo fundoplication surgery.

Collectively, these preliminary data provide compelling evidence for the potential clinical utility of CYP2C19-genotype guided dosing by documenting the relationship between CYP2C19 genotype and PPI pharmacokinetics, that response to PPI therapy, based on gastric pH, is influenced by CYP2C19 genotype, and that patients are undergoing risky, invasive procedures who may simply need a higher dose of PPI to overcome their RM phenotype status.

#### **STUDY DESIGN\_ Focus on Aim2 for Nemours Children's Hospital**

**Aim 2: Implement pharmacogenetic testing of the CYP2C19 gene-PPI drug pair in adults at UF Health and in children at Nemours Children's Hospital in the context of a comparative effectiveness genotype-supported vs. conventional PPI dosing trial.**

Overview. We have designed a comparative effectiveness clinical trial testing conventional PPI dosing with genotype-supported dosing with clinically meaningful outcomes to determine the feasibility of genetic testing in a pediatric and adult setting. The primary outcome is a composite end point of upper respiratory infections pneumonia, acute gastroenteritis, adverse kidney effects and bone fractures.

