Study Design. The study is a randomized, open-label, comparative effectiveness clinical trial in 180 patients (60 children, 120 adults) with GERD or any stomach acid mediated condition that will require a PPI. Patients will volunteer to be randomized to either conventional PPI treatment or genotype-supported PPI treatment. All participants will have symptoms of GERD or related diseases who are candidates for PPI therapy or who are on PPI therapy and classified as refractory GERD. Adult patients will be enrolled at UF Health Gastroenterology Clinics and children will be enrolled at the Nemours Children's Hospital Gastroenterology Clinics. After obtaining informed consent, participants will be genotyped and randomly assigned to either conventional treatment or genotype-supported PPI therapy using a randomization table. At NCH, study participants in the control/conventional arm will be blinded on CYP2C19 metabolizer status. Study staff members will not be blinded to any study procedures or determinations as this will improve and facilitate study feasibility. At the end of study period (i.e. 8-12 weeks) study participants in the control/conventional arm will be revealed of metabolizer phenotype status. We will also collect data from the health records for up to 24 months after enrollment on upper respiratory infection (cold), sore throat, strep throat, bronchitis, pneumonia, ear infection, acute sinusitis (sinus infection), bone fractures, renal function, and gastrointestinal infections for preliminary assessment of the effects of CYP2C19-supported PPI dosing on adverse effects.

Participation stipends. Each participant will receive \$25 dollars at the end of study participation. Participants must have completed all study procedures by the end of the study period in order to receive the complete study stipend. If a study participant decides to withdraw from study before the end of study period (before 3 months), the participant will receive a pro-rated stipend. A deposit will be provided in a single CT Payer master card. Each participant will be provided a CT Payer (master card) at the moment of consent. The CT Payer card will be uploaded with the stipend at the end of study participation. Participants whom insurance coverage is limited, a separate deposit will be provided to cover study therapy expenses. We expect to incur in study drug expenses for participants with higher PPI dose prescriptions than conventional dosing (i.e. RMs and UMs).

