Genetic results and clinical decision support. Results will be entered in the participant's electronic health record; genotype results for participants in the control/conventional arm will not be made available to patients/families through the secure patient portal in the EMR to maintain blind status. PPI recommended dosing will be made available to GI providers in the EMR for genotype-guided dosing. PPI templates will include phenotype, genotype, dosing recommendations, and educational information. Participants in the conventional arm will be prescribed the conventional PPI dose.

To minimize risks associated with genetic studies, all results of genetic tests and patient data will be stored in a secure database which is accessible only to study investigators. Genotype and phenotype data will be stripped of all identifiers prior to submission to the NIH dbGAP repository.

Assessment of PPI adverse events and efficacy. Our primary outcome will be a directed interview and questionnaire by study personnel at baseline and every following week up to 12 weeks of participation for efficacy of PPI therapy and for adverse outcomes for the study period: upper respiratory infection (cold), sore throat, strep throat, bronchitis, pneumonia, ear infection, acute sinusitis (sinus infection), and gastroenteritis. We have experience using the questionnaire to evaluate the safety of PPI treatment in children. The prevalence of each respiratory and gastrointestinal symptom will be compared in participants receiving conventional vs. genotype-supported dosing. As secondary outcomes, the efficacy and safety (adverse event score) of PPI therapy will be determined from scores from patient and parent-proxy reported outcomes: the GASP-Q, the validated SN-5 Pediatric Sinonasal Symptom Survey and validated PedsQL™ Gastrointestinal Symptoms Module. Efficacy and adverse events questionnaires will be completed via an electronic questionnaire on a weekly basis and stored in REDCap.

At Nemours Children's Hospital continuous monitoring on study metrics will be offered by study staff. Study metrics will include Gasp-Q, PedsQL™ Gastrointestinal Symptoms Module, SN-5 Pediatric Sinonasal Symptom Survey and Safety Q.

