- Gastrointestinal problems under scope includes; stomach pain and hurt; stomach upset; food and drinks limits; trouble swallowing; heartburn and reflux; gas and bloating; constipation; diarrhea; worry; medicines and communication will be measured.
- On the other hand; sinus infection; nasal obstruction; allergy symptoms; emotional distress; activity limitations and overall quality of life are some of the metrics to be evaluated for sinus and/or nasal problems.
- Each metric has its own scoring scale. Gastrointestinal problems will range from 0-100 for "Never" to "Almost always", respectively. Sinus and/or nasal problems have a 1-7 scale for "None of the time" to "All of the time", respectively.
- Safety Assessment (adverse event score) of PPI therapy will be scores from a questionnaire comprised of 7 respiratory symptoms: upper respiratory infection (cold); sore throat; strep throat; bronchitis; pneumonia; ear infection; acute sinusitis (i.e. sinus infection)

Monitoring for adverse events will be performed by the treating medical staff, the Principal Investigators, the site investigators, and the research coordinator(s). We will follow the guidance from the Office for Human Research Protections (OHRP) DHHS: Guidance on Reviewing and Reporting unanticipated Problems Involving Risks to Subjects or Others and Adverse Events <http://www.hhs.gov/ohrp/policy/AdvEvntGuid.htm>. Any event that: (1) involves harm, or an increased potential for harm, to one or more participant(s), or others, AND (2) is unexpected, AND (3) is related, or probably related, to study procedures will be reported to the Nemours and or UF IRB within 5 days of discovery, or within 24 hours if an unforeseen death. We will follow FDA guidelines for report of adverse events to the FDA within the required timeframe for the event. Additional standard institutional IRB reporting guidelines for adverse event reporting will also be followed.

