Statistical analysis. We will have two primary hypotheses tested in this pragmatic clinical trial: 1. Hypothesis: RMs (1 or 2 GOF alleles) in the genotype-supported arm have better GERD control than RMs in the usual care group 2. Hypothesis: PMs (1 or 2 LOF alleles) in the genotype-supported group have fewer adverse effects (composite of URI/GI infections, kidney adverse effects, bone fracture) than PMs in the usual care group. Continuous variables will be compared between the genotype-supported group and the usual care group using t-test, and categorical variables will be compared using the chi-squared test. The hypotheses will be tested by logistic regression analysis to estimate the odds ratios and 95% confidence intervals for GERD control rate in the RM patients between the two arms and for the adverse events between the PM patients between the two arms. Time to-event analysis will be performed using Kaplan Meier method and a Cox regression model. Significant covariates associated with the events will be adjusted for in the multivariable models. All analysis will be performed in SAS 9.4 (Cary, NC).

We will also have a composite analysis that is conducted in the same manner that combines efficacy and safety and tests the hypothesis that genotype supported PPI dosing leads to better PPI efficacy and safety, as determined by composite of refractory GERD, and adverse effects.

Finally, we will evaluate the influence of genotype-supported dosing recommendations and will evaluate the percentage of the time when a dosing recommendation was made and accepted by the treating clinician, to provide practical data on the willingness of clinicians to adopt this approach. We will also collect patient- and provider-level survey data on attitudes about pharmacogenetics testing; using survey tools adapted from those utilized by other IGNITE groups. These will be shared for network-wide analyses, but because of the number of patients we will study, we should also have sufficient data to perform analyses on our patients along.

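### The Nemours protocol defines its primary outcome in three ways that do not agree, and gives no rule for which result, or combination of results, counts as success.

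*Combined protocol and SAP*

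**What the plan says.** All of the following is current text of the Nemours protocol.

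- **Study Design, Overview:** "The primary outcome is a composite end point of upper respiratory infections pneumonia, acute gastroenteritis, adverse kidney effects and bone fractures". No subgroup and no time window are given.
- **Assessment of PPI adverse events and efficacy:** here a different primary is declared, namely "Our primary outcome will be a directed interview and questionnaire by study personnel at baseline and every following week up to 12 weeks". This covers efficacy and a list of conditions ending "bronchitis, pneumonia, ear infection, acute sinusitis (sinus infection), and gastroenteritis"; kidney effects and fractures are not on it. The same paragraph continues: "As secondary outcomes, the efficacy and safety (adverse event score) of PPI therapy will be determined from scores from patient and parent-proxy reported outcomes".
- **Statistical analysis:** "We will have two primary hypotheses tested in this pragmatic clinical trial". The first is better GERD control in rapid metabolizers (RMs, one or two gain-of-function alleles). The second is fewer adverse effects in poor metabolizers (PMs, one or two loss-of-function alleles). An efficacy-plus-safety composite is added, neither called primary nor given an alpha.
- **Power calculation:** 80% power at alpha 0.05 for each of the two hypotheses, with 600 participants.
- **Specific Aims, Aim 2:** efficacy is expected to be equivalent between arms, with fewer adverse outcomes.
- **Study Design:** 180 patients (60 children, 120 adults). Health records are searched for up to 24 months for infections, fractures and renal function, "for preliminary assessment of the effects of CYP2C19-supported PPI dosing on adverse effects".
- **Safety Assessment bullet:** the adverse event score comes from "a questionnaire comprised of 7 respiratory symptoms".

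**The concern.** A primary outcome fixes in advance which comparison decides the trial. Here the overview points to one safety endpoint in all patients, the assessment section to a mixed efficacy and safety questionnaire, and the analysis section to two subgroup tests. A team following the plan faithfully could report any of these as the primary result. If they disagree, nothing in the text says which one counts. The direction of the efficacy claim is also unsettled, because Aim 2 expects equivalence while the analysis tests superiority. What is at stake is protection against choosing the favourable result afterwards, and a type I error rate that can be stated.

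**Working it through.** **1. The three statements side by side**

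| Section | Endpoint | Population | Window |
|---|---|---|---|
| Overview | Five-part adverse-event composite | Not restricted | Not stated |
| Assessment | Efficacy plus seven respiratory conditions and gastroenteritis | Not restricted | Weekly to 12 weeks |
| Statistical analysis | (1) GERD control; (2) adverse-effect composite | (1) RMs; (2) PMs | Not stated |

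The second hypothesis uses essentially the overview's composite, although it does not name pneumonia. Restricting it to PMs makes it a different test, and GERD control is an additional primary.

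**2. Error rate and joint power**

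Inputs: alpha 0.05 and power 80% for each hypothesis (Power calculation). RMs and PMs do not overlap, because the text under Table 1 keeps \*2/\*17 carriers out of the primary analysis. Treating the two tests as independent is therefore reasonable.

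- Success if either is significant: 1 − (1 − 0.05)² = 1 − 0.9025 = 0.0975. Bound without independence: 0.05 + 0.05 = 0.10.
- Success only if both are significant: type I error is not inflated, but joint power is 0.80 × 0.80 = 0.64.

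**3. The plan's power figures**

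The 80% figures cannot be reproduced directly, because no control rate is stated. I solved for the rate that gives 80% (two-sided test of two proportions, pooled variance):

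- RMs: 33% of 600 = 198, or 99 per arm. A relative risk of 1.35 gives 80% only if usual-care GERD control is about 54% (about 50% if one-sided).
- PMs: 89 per arm as stated. A 29% reduction gives 80% only if the usual-care adverse-event rate is about 70% (about 64% if one-sided).
- The 178 PMs are 178/600 = 29.7%. Table 1 gives 20% + 1.7% = 21.7%, hence 600 × 0.217 = 130.

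Taking the two-sided implied control rates as assumptions:

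| Sample | RM per arm | Power | PM per arm (29.7%) | Power | PM per arm (21.7%) | Power |
|---|---|---|---|---|---|---|
| 600, alpha 0.05 | 99 | 80% | 89 | 80% | – | – |
| 600, alpha 0.025 | 99 | 71% | 89 | 71% | – | – |
| 180, alpha 0.05 | 29.7 | 33% | 26.7 | 33% | 19.5 | 25% |
| 60 children, alpha 0.05 | 9.9 | 13.5% | 8.9 | 13.5% | 6.5 | 11% |

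At 0.025 each, restoring 80% would need about 121 RMs and 108 PMs per arm.

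**4. Sources for the composite**

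- Absent from the seven-item safety form: gastroenteritis, kidney effects, fractures.
- Absent from the weekly interview list: kidney effects, fractures.
- Absent once the record review is counted: none.

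Infections therefore have two possible sources, a 12-week interview and a 24-month record search, while kidney effects and fractures have only the second. No rule says which source and window define an event.

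**The case against.** The best defence is that the statements overlap more than they conflict. The second hypothesis largely repeats the overview's composite, and event prevalence as primary with questionnaire scores as secondary need not be a contradiction. The plan also requires trial registration, where one primary may be named. Part of the text that follows the overview was not available to me, so a success rule placed there cannot be excluded. These points narrow the matter but do not remove it: the available sections still disagree on population, on whether efficacy is primary, and on components and window.

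A reader might infer three stronger things that the documents do not support.

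- *Three of the five composite parts go uncollected.* That describes only the seven-item form, which supplies the adverse event score that the assessment section calls secondary. The interview list includes gastroenteritis, and the record review covers GI infections, renal function and fractures.
- *Three tests each run at 0.05, giving 1 − 0.95³ = 14.3%.* The alpha is stated for two hypotheses only. The third composite is not called primary, and it overlaps the other two, so it is not independent of them.
- *The adverse-event test rests on 60 × 0.217 = 13 carriers.* That assumes a children-only test. The Nemours text describes one trial of 180 and powers the hypothesis on the combined sample; 180 × 0.217 is about 39.

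Nor do the documents show which hypothesis should lead. GERD control in RMs would rest on about 60 × 0.33 = 20 children at Nemours alone, and Aim 2 expects equivalent efficacy.

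**Conclusion.** The inconsistency is real and the plan is wrong as written: followed literally, it has no determinate primary result. An either-suffices reading carries a 9.75% type I error, resting on the stated alpha of 0.05 per test and on independence between non-overlapping subgroups. A both-required reading carries about 64% joint power, resting on the plan's own 80% figures. Those figures belong to 600 participants. At 180, power is about 25% to 33% per hypothesis if the implied control rates of 54% and 70% hold; those rates are my back-calculation, not the plan's. On data collection, the defect is limited to unreconciled sources and windows and to the gastroenteritis item that the interview list has and the form lacks.

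**What to change.** Amend the overview, the assessment section, the safety bullet and the statistical analysis section so that all state the same primary endpoint, with instrument, population and window.

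1. Either name one primary and make the rest secondary, or keep both hypotheses in a fixed testing order or at 0.025 each. Which hypothesis leads is the sponsor's choice.
2. Settle whether the efficacy claim is equivalence, as in Aim 2, or superiority, as in the analysis section.
3. Call the efficacy-plus-safety composite secondary.
4. Give one window and one data source for each part of the adverse-event composite, and add gastroenteritis to the weekly form to match the interview list.
5. Restate power for the chosen primary at 180 (60 children), with the control rate, sidedness and subgroup share written down.

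The cost is protocol wording, one item on an existing electronic form and a stated power well below 80% on the assumptions used here. If both hypotheses are kept at 0.025, power at 180 is about 23% each on the same assumptions (29.7 RMs and 26.7 PMs per arm).
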